	(CTCs) by comparing master regulators generated from
	CTCs to those obtained from tumor tissue in matched
	pre- and on-treatment samples with an OncoTreat-
	informed agent.
•	Identify associations between master regulator profiles
	and additional clinical, epidemiological, physiological,
	imaging, or molecular features of the subject or subject's
	tumor.
•	Identify potential biomarkers, beyond the master
	regulator signature, using additional genomic, RNA,
	protein, and imaging platforms that are predictive or

	prognostic of response to each OncoTreat-prioritized agent.
Number of Subjects	We will enroll 30 subjects in Part 1 (AAAR6703) of the study to obtain detailed predicted therapy options. We anticipate accrual over 15-18 months. We estimate that 15 subjects will progress to Part 2, requiring an additional 15-18 months to complete treatment and for follow-up.
Diagnosis and Main Inclusion Criteria	Locally advanced, unresectable or metastatic pancreatic cancer who progressed on one or two prior lines of chemotherapy, for whom a precision therapy was recommended in Part 1.
Duration of administration	Treatment will continue until progressive disease, unacceptable adverse events, intercurrent illness that prevents further administration of treatment, investigator's decision to withdraw the subject, subject withdrawal of consent, pregnancy of the subject, noncompliance with trial treatment or procedure requirements, or administrative reasons requiring cessation of treatment.
Reference therapy	Not applicable – single arm study.

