4.2 Number of Patients

Thirty subjects will be enrolled on Part 1 and, therefore, up to a maximum of 30 subjects will receive OncoTreat-prioritized agents on Part 2. No subjects will be replaced.

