10.2 Definitions

Evaluable for toxicity: All patients will be evaluable for toxicity from the time of their first treatment with an OncoTreat-prioritized agent.

Evaluable for objective response: Only those patients who have measurable disease present at baseline, have received at least one cycle of therapy, and have had their disease re-evaluated will be considered evaluable for response. These patients will have their response classified according to the definitions stated below. (*Note*: Patients who exhibit objective disease progression prior to the end of cycle 1 will also be considered evaluable.)

Evaluable for feasibility – primary outcome: All subjects who receive a single dose of study drug will be included in the primary outcome analysis of feasibility.

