12. STATISTICAL CONSIDERATIONS

This is a single arm, phase Ib study with 2 co-primary endpoints:

- Feasibility: The primary objective of this trial is to determine the feasibility of the OncoTreat platform in guiding therapy. The primary outcome is whether a subject begins therapy on Part 2. Previous attempts to match subjects based on DNA profiling have yielded enrollment rates of 3-5% [14, 78]. We hypothesize that we will validate OncoTreat matches for 50% of subjects and that at least 30% of enrolled subjects (60% of matches) will begin therapy on Part 2. With 30 enrolled patients on Part 1, we will have 80% power to detect a treatment rate of 30% on Part 2 compared to a historical treatment rate of 5% with alpha of 0.05. We will also assess the "match rate" the fraction of patients who match with at leaset one drug. With 30 enrolled subjects, we will have 97% power with alpha = 0.05 to detect a 50% match rate (15 of 30 subjects) compared to a (liberal) estimated match rate of 20% based on DNA profiling in PDA.
- Efficacy: The primary clinical efficacy endpoint is the **objective response rate (ORR)** for OncoTreat-prioritized drugs, which corresponds to the number of patients whose tumors demonstrate a 30% or greater reduction from baseline in the sum of the diameters of all target lesions amongst all evaluable patients, as assessed by standard-of-care CT scans. We target estimating the ORR and the corresponding 95% confidence interval.

Secondary endpoints will include: 1) **disease control rate (DCR) at 16 and 24 weeks**, which corresponds to the number of patients whose tumors demonstrate either an objective response or stable disease, defined as a no more than 20% increase from baseline in the sum of the diameters of all target lesions; 2) **median progression-free survival (mPFS)**, defined as the median duration prior to the development of disease progression or patient death; 3) **overall survival (OS)**, defined as time from first dose of OncoType-informed drug to death due to any cause; and 4) **safety and tolerability**, defined as the incidence of Grade 3/4 AEs in terms categorized and graded according to NCI CTCAE v4.0. We will estimate DCR, mPFS, and OS and their 95% confidence interval.

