The phase III trial (NAPOLI-1) that resulted in the FDA-approval of nanoliposomal irinotecan and 5-fluorouracil in the second-line setting demonstrated a median overall survival of 6.1 months versus 4.2 months for 5-fluorouracil monotherapy (primary endpoint), mPFS of 3.1 months, and an ORR of 16% (compared to 1% in the 5-fluorouracil arm) [7]. Fifty-one (12%) patients had not had previous treatment for metastatic disease, 234 (56%) had received one previous line of metastatic treatment, and 132 (32%) had previously received two or more lines of metastatic treatment. The disease control rate was less than 20% and did not differ between treatment groups. Thus, based on historical controls, the ORR for treatment-resistant metastatic PDAC is expected to be no more than 16%.

Using the above mentioned rates, a sample size of n = 9 achieves at least a 80% power to detect a difference of 25% in ORR (30% vs 5%) using a one-sided binomial test with a target alpha of 0.1. To be conservative, we use the minimum number of patients (9) expected to be treated in this calculation. If at the end of the study the total number of objective responses is greater than or equal to 2, we will be able to reject the historical rate of 5% at the significance level of 0.05 with power of 69% and OncoTreat will have demonstrated a clear signal of clinically meaningful improvement in the primary endpoint for patients with advanced, previously-treated PDA. Assuming about 30% of enrolled patients will receive an OncoTreat-informed treatment, N = 30 subjects is an appropriate sample size for this prospective study.

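### The response-rate success rule (2 or more responses) does not have the stated level of 0.05 and 69% power: at n = 9 its exact one-sided alpha is 0.071 and its power 80.4%, and with no denominator its alpha passes 0.1 from 11 evaluable patients

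*Combined protocol and SAP*

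**What the plan says.** The clinical co-primary endpoint is the objective response rate (ORR). Section 12, Statistical Considerations, sizes it at n = 9 for an ORR of 30% against 5%, with at least 80% power, "using a one-sided binomial test with a target alpha of 0.1". Later in the same paragraph it sets the success rule: if total responses at the end of the study are 2 or more, "we will be able to reject the historical rate of 5% at the significance level of 0.05 with power of 69"%. A pass is described in advance as a clear signal of clinically meaningful improvement. The Statistical Methodology part of the synopsis repeats the paragraph.

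The rule names no number of patients. Elsewhere the documents say:

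- Section 12, on the nine: "we use the minimum number of patients (9) expected to be treated in this calculation". This follows from the assumption that "at least 30% of enrolled subjects (60% of matches) will begin therapy on Part 2", and 30% of 30 is 9.
- Synopsis, Number of Subjects: "We estimate that 15 subjects will progress to Part 2".
- Section 4.2: "up to a maximum of 30 subjects will receive OncoTreat-prioritized agents on Part 2", with no replacement.
- Section 12 measures response "in the sum of the diameters of all target lesions amongst all evaluable patients". Under Section 10.2, patients with measurable disease who "have received at least one cycle of therapy, and have had their disease re-evaluated will be considered evaluable for response"; those who progress before the end of cycle 1 also count.

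**The concern.** One paragraph gives a single rule two levels (0.1 and 0.05) and two powers (at least 80% and 69%). Both pairs cannot be right for the same cutoff, null, alternative and sample size.

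Separately, a fixed count of responses defines a test only when the number of patients is fixed. Here it is not: it may fall below 9 through non-evaluability or rise above 9 through a higher treatment rate. Taking the minimum n is conservative for power, but not for the false-positive rate of a fixed count, which rises with each added patient.

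This is the only pass/fail rule for the clinical co-primary endpoint. As written, 2 responses in 9 would be reported as significant at 0.05 when the exact one-sided p-value is 0.071. If 15 were evaluable, 2 responses would be reported as a rejection at p = 0.171, above even the looser 0.1.

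**Working it through.** **Inputs (Section 12).** Null ORR 0.05, alternative 0.30, n = 9, one-sided binomial test, cutoff 2 or more responses.

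**Formula.** P(X ≥ 2) = 1 − (1−p)^n − n·p·(1−p)^(n−1).

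**The plan's first sentence (alpha 0.1, power at least 80%).**

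- Alpha at n = 9: 1 − 0.95^9 − 9(0.05)(0.95^8) = 1 − 0.6302 − 0.2985 = 0.0712.
- Power at n = 9: 1 − 0.70^9 − 9(0.30)(0.70^8) = 1 − 0.0404 − 0.1556 = 0.8040.

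This sentence reproduces: alpha is within 0.1 and power is above 80%.

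**The plan's second sentence (level 0.05, power 69%).** It does not reproduce. To hold 0.05 at n = 9 the cutoff must be 3 or more, with alpha 0.0084 and power 0.5372. Neither neighbouring smaller n gives the stated pair: n = 7 gives 0.0444 and 67.1%, n = 8 gives 0.0572 and 74.5%, and the documents use neither. Some approximations for a nominal one-sided 0.05 test at n = 9 come close to 69% (continuity-corrected normal 68.8%, arcsine 68.4%). That may be where the figure arose, but it is inference, and these are not the error rates of the written rule.

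**The same cutoff at other numbers evaluable.**

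| n | Alpha of 2 or more (ORR 5%) | Power (ORR 30%) |
|---|---|---|
| 7 | 0.044 | 67.1% |
| 8 | 0.057 | 74.5% |
| 9 | 0.071 | 80.4% |
| 10 | 0.086 | 85.1% |
| 11 | 0.102 | 88.7% |
| 15 | 0.171 | 96.5% |
| 30 | 0.447 | >99.9% |

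Alpha first exceeds 0.05 at n = 8 and 0.1 at n = 11.

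**How likely the larger n are.** Assumption: each of the 30 enrolled is independently treated and evaluable with probability q, so n follows Binomial(30, q).

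- q = 0.30, the plan's treatment rate: P(n ≤ 8) = 43%, P(n ≥ 11) = 27%, P(n ≥ 15) = 1.7%; average alpha 7.4%, average power 76.6%.
- q = 0.50: P(n ≥ 11) = 95%; average alpha 17.2%.

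**Cutoff tied to n at one-sided 0.1.** The smallest cutoff with exact alpha at or below 0.1 is 2 for n up to 10, 3 for n = 11 to 22, and 4 for n = 23 to 30. The largest alpha is 0.0948, at n = 22. Averaged at q = 0.30, alpha is 4.7% and power 72.1%.

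**Intervals for 2 of 9 (Clopper-Pearson).** 95%: 2.8% to 60.0%. 80%: 6.1% to 49.0%.

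**Against the 16% figure.** Section 12 expects a historical ORR of no more than 16%. At a true ORR of 16%, 2 or more passes with probability 0.435 at n = 9 and 0.718 at n = 15.

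**The case against.** Four points can be made for the plan.

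1. The cutoff or n, rather than the level, could be the slip. An exact 0.05 test with 3 or more of 11 has power 68.7%, which rounds to 69%. But the documents never give n = 11, and the written cutoff of 2 with n = 9 matches the paragraph's own one-sided 0.1 design. Keeping the cutoff and correcting the level is therefore the smaller change. If the sponsor does want 0.05, a different table applies (see the fix).

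2. Fifteen evaluable patients is not the plan's expectation for treatment. Section 12 has 50% of 30, or 15, matching and 60% of those, or 9, starting therapy, so the synopsis figure of 15 may be a count of matches. This stands as a limit on size: at the 30% rate the average alpha is 7.4%, below 0.1, and the 30-patient case is an extreme. It does not supply the missing denominator, and 11 or more still has a 27% chance.

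3. The trial is an early single-arm study that also plans a 95% confidence interval. A reader would see that the interval for 2 of 9 includes 5%. That softens the harm, but the interval would then sit beside a claimed rejection at 0.05.

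4. The 5% null may be reasonable, and 16% comes from a combination arm and is used as an upper bound. Both are fair. Section 12 gives no source for 5%, but response rates in Sections 3.6 to 3.8 (3 of 42; none; 6.5% and 3.4%) make it plausible, although those populations and regimens differ from this trial's. This part is advisory only.

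**Conclusion.** The concern holds. At the plan's own n = 9, the rule of 2 or more responses has exact one-sided alpha 0.071 and power 80.4%, not 0.05 and 69%. That result needs no assumption beyond the stated binomial test.

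The missing denominator is a second defect: alpha exceeds the design's 0.1 from 11 evaluable patients. Its practical size depends on how many are treated and evaluable. Average alpha is 7.4% at the planned 30% rate and 17.2% at 50%, under the independence model used here.

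Because this is the only decision rule for the clinical co-primary endpoint, it must be corrected. A pass rejects an ORR of 5%. With a 43% chance of passing at n = 9 when the true ORR is 16%, it does not by itself show clinically meaningful improvement.

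**What to change.** **Required, in both the synopsis and Section 12:**

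1. Replace the level of 0.05 and power of 69% with: one-sided exact alpha 0.071 and power 80.4% (30% versus 5%) at n = 9.
2. Tie the cutoff to the number evaluable at one-sided 0.1: 2 or more for n of 10 or fewer, 3 or more for n = 11 to 22, 4 or more for n = 23 to 30. Alternatively, report the exact one-sided p-value at the actual n. If the sponsor prefers 0.05, the cutoffs are 3 or more for n = 8 to 16, 4 or more for n = 17 to 28, and 5 or more for n = 29 to 30, with power 53.7% at n = 9.

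**Secondary:**

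3. Word a pass as rejecting an ORR of 5% at one-sided 0.1, and give the matching two-sided 80% interval beside the planned 95% interval. At the 0.1 cutoffs the 80% lower limit always exceeds 5% (lowest 5.1%, at n = 22). The 95% lower limit falls below 5% at n = 6 to 10 and 14 to 30, as expected with a one-sided 0.1 test.
4. Do not describe a pass as clinically meaningful improvement on this test alone; report the 43% pass probability at an ORR of 16% (n = 9).
5. Advisory: state the source of the 5% null.

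**Cost.** Wording only, and no extra patients, but the stated level is less favourable and some power is lost. Under the tied cutoff, power at n = 11, 12 and 13 is 68.7%, 74.7% and 79.8%, against 88.7%, 91.5% and 93.6% with the fixed count. At n = 8 or fewer it is below 80% under either rule. Averaged over the 30% treatment rate, power goes from 76.6% to 72.1% and the false-positive rate from 7.4% to 4.7%.

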13. PROTECTION OF HUMAN SUBJECTS

This study is to be conducted in accordance with applicable government regulations and Institutional research policies and procedures.

This protocol and any amendments will be submitted to a properly constituted Institutional Review Board (IRB), in agreement with local legal prescriptions, for formal approval of the study conduct. The decision of the IRB concerning the conduct of the study will be made in writing to the investigator and a copy of this decision will be obtained before commencement of this study.

All subjects for this study will be provided a consent form describing this study and providing sufficient information for subjects to make an informed decision about their participation in this study. This consent form will be submitted with the protocol for review and approval by the IRB for the study. The formal consent of a subject, using the IRB-approved consent form, must be obtained before that subject is submitted to any study procedure. This consent form must be signed by the subject or legally acceptable surrogate, as outlined in the IRB approved protocol, and the investigator-designated research professional obtaining the consent.

14. STUDY FINANCES

14.1 Conflict of Interest

Any investigator who has a conlict of interest with this study (patent ownership, royalities, or financial gain greater than the minimum allowable by their institution, etc.) must have the conflict reviewed by the Columbia University Conflict of Interest Committee with a Committee-

sanctioned conflict management plan that has been reviewed and approved prior to participation in this study. All CUMC investigators will follow the University conflict of interest policy.

14.2 Subject Stipends or Payments

There are no subject payments or stipends.

17. APPENDICES

17.1 Appendix A: Eastern Cooperative Oncology Group (ECOG) Performance Status

Grade	Description
0	Normal activity. Fully active, able to carry on all pre-disease performance without restriction.

1	Symptoms, but ambulatory. Restricted in physically strenuous activity, but ambulatory and able to carry out work of a light or sedentary nature (e.g., light housework, office work).
2	In bed <50% of the time. Ambulatory and capable of all self-care, but unable to carry out any work activities. Up and about more than 50% of waking hours.
3	In bed >50% of the time. Capable of only limited self-care, confined to bed or chair more than 50% of waking hours.
4	100% bedridden. Completely disabled. Cannot carry on any self-care. Totally confined to bed or chair.
5	Dead.

* As published in Am. J. Clin. Oncol.: Oken, M.M., Creech, R.H., Tormey, D.C., Horton, J., Davis, T.E., McFadden, E.T., Carbone, P.P.: Toxicity And Response Criteria Of The Eastern Cooperative Oncology Group. Am J Clin Oncol 5:649-655, 1982. The Eastern Cooperative Oncology Group, Robert Comis M.D., Group Chair.

17.2 Appendix B: NCI Common Terminology Criteria for Adverse Events (CTCAE) V4.0 Grading Scale

The descriptions and grading scales found in the revised NCI Common Terminology Criteria for Adverse Events version 4.0 will be utilized for adverse event reporting.

http://www.oncology.tv/SymptomManagement/NationalCancerInstituteUpdatesC TCAEtov403.a spx

17.3 Appendix C: Response Evaluation Criteria in Solid Tumors (RECIST) 1.1

Criteria for Evaluating Response in Solid Tumors RECIST version 1.1 will be used in this study for assessment of tumor response. While either CT or MRI may be utilized, as per RECIST 1.1, CT is the preferred imaging technique in this study.

In addition, volumetric analysis will be explored for response assessment.

17.4 Appendix D: Preclinical Studies – PDX/PDO Analyses

The initial biopsy from each newly diagnosed, treatment-naïve subject will be used both for OncoTreat profiling and to establish orthotopic PDX and/or PDO models from each patient in NSG mice (from an established NSG breeding colony). After outgrowth of the primary tumor/organoids, a portion will be banked and the bulk tumor dissected into 1-2 mm cubes for orthotopic re-implantation [79] into NSG recipients. For each primary tumor, we will evaluate a minimum of 6 and up to 10 candidate OncoTreat regimens and 2 controls (gemcitabine and vehicle). For each treatment, we will implant 8 tumors (5 for survival, 3 for PD analysis) plus 6 extra in case any fail to engraft (total = 70).

Tolerable schedules in mice for top-predicted drugs from our preliminary analysis have been developed. Additional agents will be assessed during the period when PDX/O models are engrafting, relying on a combination of published data and experimental assessments in mice using a dose escalation format and daily health, weight, and behavior assessments.

Upon reaching 150 mm³, tumors will be enrolled and randomized to a treatment arm and treated until the animal meets endpoint criteria (based on a scoring system). Tumor volumes will be monitored twice weekly by 3D ultrasound [80]. The **primary endpoint** will be response rate, as determined by ultrasound-measured tumor volumes. In our (The [name] Laboratory) experience, replicate tumors from the same donor tend to respond uniformly to treatment, making 5 animals sufficient for analysis of response rate and allowing us to evaluate more regimens from one donor sample.

Three animals per treatment group will be euthanized 24 hours after receiving their third treatment dose for assessment of pharmacodynamics response. RNA-seq will be performed on bulk tissue samples, with computational filtering for human reads to assess effects on the epithelial compartment. VIPER analysis will be performed on the tumor profiles to determine whether the treatment reversed the activity of the predicted MRs relative to vehicle-treated tumors. In addition, tumor histopathology will be analyzed by [name] in the Department of Pathology. Immunohistochemistry (IHC) will also be performed to assess proliferation (Ki-67, phospho-histone H3) and apoptosis (cleaved caspase 3) [81, 82].

17.5 Appendix E: LC-MS/MS Method Specimen/Sample Type: Serum

Volume: 300µL

Sample Stability: all analytes are stable in serum samples at room temperature for 5 hours, at 4-8 °C for 3 days, and at -80 °C for at least 60 days.

Instrument and materials:

- ACQUITY Xevo TQ-D with ACQUITY UPLC® CSH C18 3.0x100mm 1.7 µm column (Waters Corporation)
- Single-channel pipettes: 20µl, 100µl,200µl and 1000µl air displacement pipettes
- Vortex mixer
- Centrifuge
- Vials Waters Acquity UPLC H-Class System and H-Class Bio System
- Eppendorf Centrifuge 5427 R
- Balance Mettler Toledo AL54

Sample preparation – extraction by protein precipitation

- 1- In a 1.5 ml eppendorf tube add 120 μl sample (blank, double blank, calibrators, QC low, QC middle, QC high, and patient samples)
- 2- Add 10 µl ISTD working solution
- 3- Add 500 µl methanol
- 4- Mix with vortex for 5 min
- 5- Centrifuge at 14000 rpm, 15 °C, for 15 min
- 6- Take 240 μl supernatant and transfer into an UHPLC autosampler vial containing 200 μl water and mix.
- 7- Place the samples in the autosampler of the instrument and start the analytical run. 10ul of each sample will be injected for LC-MS/MS analysis.

Mobile Phase Preparation:

- **1.** 2M ammonium acetate in water (stock):
 - 77.08g ammonium acetate
 - 500 ml water (use up 6 months of being prepared)
- **2.** Mobile Phase A:
 - 2mM ammonium acetate and 0.1% formic acid (v/v) in water
 - 1.0 ml 2M ammonium acetate solution (above step 1)
 - 1.0 ml Formic acid
 - 998 ml optima grade water
- **3.** Mobile Phase B: 2mM ammonium acetate and 0.1% formic acid (v/v) in methanol
 - 1.0 ml 2M ammonium acetate solution (above step 1)
 - 1.0 ml Formic acid
 - 998 ml optima grade Methanol
- 4. Wash Solvent: 50% optima grade acetonitrile / 50% optima grade water
- 5. Needle Wash: 25% optima grade methanol / 25% optima grade acetonitrile / 50% optima grade 2-propanol
- 6. Seal Wash: 80% optima grade water / 20% optima grade methanol

Liquid Chromatography settings

File name of inlet method: Assay extension II.acm/.ftn/.qsm

Time (min)	Flow (ml/min)	% A	%В	Curve
0	0.500	85	15	6
0.5	0.500	85	15	6
1.20	0.500	60	40	6
5.00	0.500	5	95	6
5.2	0.500	5	95	6
5.21	0.500	85	15	6
5.50	0.500	85	15	11

Xevo TQD Settings

Ion Mode: ESI(+) Capillary Voltage: 1.10 kV Source Temperature: 150°C Desolvation Gas Temperature: 600°C Cone Gas Flow: 50 L/Hr Desolvation Gas Flow: 900 L/Hr MS Mode: Multiple Reaction Monitoring (MRM)
